4.1 Definition of Baseline

The primary analysis of the study focuses on the results of the Double-Blind Treatment Period. Therefore, baseline for the primary analysis will be defined as the randomization visit, i.e. the start of the Double-Blind treatment period. This baseline will be referred to as Randomization (Visit).

For the analysis of safety, baseline is defined as the start of the Open Label Period for *de novo* and 12709A rollover patients. This baseline will be referred to as Baseline (Visit). For 12712A rollover patients baseline will be defined as the start of the Double-Blind Treatment Period, i.e. the randomization visit.

4.2 Definition of Periods

The following periods can be identified:

Screening period

A Screening Visit will be performed only for de novo patients. Patients rolling over from Study 12709A will proceed directly to the Baseline Visit. Therefore, the screening period is not applicable for these patients. In addition, this period is not applicable for patients rolling over from Study 12712A, as these patients will enrol the study at the randomization visit. The screening period begins when the first screening assessment is done after written Informed Assent/Consent has been obtained, and ends at the Baseline Visit for the Open Label Period (visit 2).

Open Label Period

De novo patients who continue to meet all inclusion criteria and none of the exclusion criteria (see section 5.3 of the study protocol) will be enrolled into a 12-week Open Label Period. For patients rolling over from Study 12709A, the Baseline Visit of the Open Label Period will be performed the same day as the Week 12 (Completion) Visit of Study 12709A.

Patients eligible for entering the Open Label Period will start IMP (vortioxetine) at the Baseline Visit of the Open Label Period.

The duration of the Open Label Period is 12 weeks or until the patient is withdrawn from the study, whichever comes first. If a patient withdraws from the study, the Open Label Period ends at the withdrawal visit.

Double-Blind Treatment Period

The Double-Blind Treatment Period starts at the randomization visit (visit 8) and ends after 26 weeks of treatment (visit 17), or until the patient will be withdrawn from the study, whichever comes first. If a patient withdraws from the study the Double-Blind Treatment Period ends at the withdrawal visit.

Patients rolling over from Study 12712A will have their first visit in this study at visit 8 (the Randomization Visit). For 12712A-patients the last available values from assessments and procedures (efficacy/safety, and use of concomitant medication) performed at either Visit 7 (Week 8) and/or Visit 8 (Week 10), or Visit 9 (Week 12) in Study 12712A will be the Randomization Visit values for this study.

Safety Follow-up Period

The Safety Follow-up Period has a duration of 4 weeks after the last IMP intake. This period starts at the date of last IMP intake.

A Safety Follow-up Period is planned at the end of the study (i.e. after completion of visit 17) and after withdrawal of a patient in either the Open Label Period or the Double-Blind Treatment Period. The end of the Safety Follow-up Period will be at visit 18 (SFU visit).

4.3 Definition of Withdrawal

The patients who withdraw from the Open Label Period or the Double-Blind Treatment period will be described as *withdrawn from the study*. The remaining patients will be described as *completed the study*.

5 Analysis Sets

The following analysis sets will be used to analyze and present the data:

all-patients-enrolled (APES) – all-patients-enrolled to the 12-week Open Label Treatment Period who took at least one dose of IMP

all-patients-randomized set (APRS) – all patients randomized to the 26-week Double-Blind Treatment Period

full-analysis set (FAS) – all patients randomized to the 26-week Double-Blind Treatment Period who took at least one dose of Double Blind IMP

The efficacy analyses will be based on the FAS and the safety analyses will be based on the APES (for *de novo* and 12709A rollover patients) and the APRS (for 12712A rollover patients).

The patients and data will be classified into the analysis sets according to the definitions above during a *Classification Meeting* after the study database has been released, but before the blind has been broken.

6 Descriptive Statistics

In general, summary statistics (n, arithmetic mean, standard deviation, median, minimum and maximum values) will be presented for continuous variables. Counts and, if relevant, percentages will be presented for categorical variables. The denominator for the percentage calculation will be noted.

Unless otherwise specified, data listings will include enrolment source, site, treatment group, patient screening number, sex, age, race, and baseline weight.

7 Patient Disposition

7.1 Summary of Patient Disposition

The disposition data will be summarized for the Open Label Period (split out by *de novo* patients, rollover patients from Study 12709A and total), and the Double-Blind Treatment Period (split out by treatment groups and total) separately. The number of patients in APES and APRS who completed or withdrew from the study, as well as the number of patients in each analysis set (APES, APRS and FAS) will be presented.

7.2 Withdrawals

The number of patients who withdrew from the Open Label Period will be summarized by *de novo* patients, rollover patients from Study 12709A and total. The number of patients who withdrew from the Double-Blind Treatment Period will be summarized by treatment group and total. The primary reason for withdrawal as well as all reasons for withdrawal will be presented per period.

Patients who withdrew from the study will be listed and the listing will include the number of days in the study until withdrawal from the study, the number of days on IMP, the primary reason for withdrawal, and all reasons for withdrawal.

8 Demographics and Baseline Characteristics

Summary tables on demographic and baseline characteristics will be presented for both the Open Label Period and the Double-Blind Treatment Period separately. The baseline characteristics for the Open Label Period will be based on the APES and will be presented for *de novo* patients, rollover patients (from Study 12709A) and overall.

For the Double-Blind Treatment Period the summary tables on demographics will be based on the FAS and results will be presented per treatment group (vortioxetine and placebo) and in total.

Demographics (sex, age, ethnicity and race), baseline characteristics (height, weight and BMI), disease characteristics and baseline efficacy variables will be summarized.

The following baseline (randomization) efficacy variables will be summarized:

CDRS-R total score

CGI-S score

PQ-LES-Q scores (total score and overall score (item 15))

Disease characteristics will include MDE history (MDD history, including number of MDEs, duration of current episode, treatment type (psychotherapy / pharmacotherapy) for MDD. In addition, MDD treatment will be summarized.

Medical history from the Medical History eCRF page will be coded with medical dictionary for regulatory activities (MedDRA) version 19.0 or above. All medical histories, data on major depressive disorder history and treatment, the family psychiatric history and the history of stimulant medication will be listed.

9 Recent and Concomitant Medication

Recent and concomitant medication will be coded using the WHO Drug Dictionary (WHO Global B3 Mar 2020).

Medications will be classified according to the start and stop time and summarized by anatomical therapeutic chemical (ATC) code, generic drug name:

- medication discontinued prior to first dose of IMP in Open Label Period
- concomitant medication continued after first dose of IMP in Open Label Period
- concomitant medication started at or after first dose of IMP in Open Label Period
- concomitant medication continued after first dose of IMP in Double-Blind Treatment Period
- concomitant medication started at or after first dose of IMP in Double-Blind Treatment Period
- concomitant medication started after last dose of IMP in Double-Blind Treatment Period

Concomitant medications started after withdrawal from treatment will be listed separately.

Two sets of tables will be produced; for the Open Label Period tables will be based on the APES and will present the *de novo* patients and 12709A rollover patients separately as well as in total.

For the Double-Blind Treatment Period, tables will be based on the APRS and presented per treatment group as well as overall.

10 Exposure

Exposure and compliance will be calculated per patient and summarized for Open Label Period and Double-Blind Treatment Period separately. For the Open Label Period results will be summarized for *de novo* and 12709A rollover patients separately as well as in total, whereas for the Double-Blind Treatment Period results will be presented per treatment group and overall.

Exposure (days) to IMP, irrespective of missing doses, in each period, will be calculated as:
Date of last IMP intake – Date of first IMP intake in the respective period+ 1
Exposure in weeks will be calculated as: Exposure in days/7

The calculation will include the patient years of exposure (PYE). PYE will be calculated as the sum of the number of days of exposure to IMP for each patient, divided by 365.25 days.

Compliance will be defined as the number of days in which a dose was taken related to the number of days the patient was expected to take IMP as per the protocol.

Compliance in each treatment period will be calculated as:
(the number of days of dose taken / the number of days a dose was planned)*100

Exposure and compliance will be summarized using standard summary statistics. In addition, exposure to IMP will be categorized in the following intervals:

< 1 week
1-2 weeks
3-4 weeks
5-8 weeks
9-10 weeks
11-12 weeks
>12 weeks

for the Open Label Period,
and:

< 1 week
1-2 weeks
3-4 weeks
5-6 weeks
7-10 weeks
11-14 weeks
15-18 weeks
19-22 weeks
23-26 weeks

>26 weeks relative to randomisation for the Double-Blind Treatment Period.

For the Open Label Period an overview of the dosing pattern per patient will be presented.

For both the Double-Blind Treatment Period and the Open Label Period, summary statistics on the mean daily dose will be presented. The results for the Open Label Period will be presented for *de novo* and rollover patients separately, as well as in total. For the Double-Blind Treatment Period this will only be presented for the vortioxetine treated patients.

The mean daily dose will be defined as:

Total dose received during the Double-Blind Treatment Period / number of exposure days in the Double-Blind Treatment Period.

For the Double-Blind Treatment Period a frequency count on the dosage received, including the number of patients withdrawn per dose, will be presented.

Exposure will be summarized based on the APES for Open Label Period and on the APRS for Double-Blind Treatment Period.

11 Efficacy

11.1 Overview of Planned Efficacy Analysis

An overview of all planned effectiveness analyses is provided in [Panel 3](#).

Panel 3 Overview of Planned Efficacy Analyses

Variable (Analysis Set): Endpoint	Type	Descriptive Statistics ^a		Logistic Regression		Cox Regression	ANCOVA	MMRM
		OC	LOCF	OC	LOCF			
Time to relapse (FAS)	4					X		
Relapse (FAS)	3	X		X	X			
CDRS-R (FAS) -Total score	1	X	X				X	X
PQ-LES-Q (FAS) -Total score (sum of item 1-14)	1	X	X				X	X
-Overall score (item 15)	1	X	X				X	X
CGI-S (FAS)	1/2	X	X				X	X
CGI-I (FAS) score	1/2	X	X				X	X

1 = continuous; 2 = categorical; 3 = binary; 4 = time to event

a Including summaries of absolute values and changes from randomization for endpoints based on changes

In addition to the planned efficacy analysis on the FAS, descriptive statistics and the change from randomization in the CDRS-R total score, per inclusion source, will be presented for the Open Label Period.

Also the number of relapses will be summarized descriptively according to relapse criteria: CDRS-R total score ≥ 40 with 2 weeks of clinical deterioration, investigator's judgement, or both.

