16.10 Sample Size and Power

The calculation of power is based on a log-rank test for the time to relapse at a one-sided 5% level of significance using SAS Proc Power. A sample size of 80 randomized patients (40 patients per treatment group) will provide at least 80% power to find a difference between

vortioxetine and placebo as statistically significant, when expecting cumulative relapse rates at 0.42 and 0.69 over 26 weeks, respectively corresponding to a hazard-ratio of 2.15. The assumption of relapse rates (42% and 69% over 6 months for vortioxetine and placebo, respectively) is based on observed rates from a similarly designed relapse-prevention study of fluoxetine in paediatric patients with MDD who had an adequate response after 12 weeks of acute treatment.¹⁴

It is anticipated that approximately 60% of *de novo* patients enrolled into the open-label period will qualify for the double-blind study period. To achieve 80 randomized patients, 150 patients are estimated to be enrolled into the study (depending on number and randomization rate of *de novo* and rollover patients).

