3.1 Open Label Period

*Open Label Period (for *de novo* patients and rollover patients from Study 12709A)*

- The duration of the open-label, flexible-dose treatment period will be 12 weeks.
- The dosage of vortioxetine will be initiated at 5 mg/day for the first 2 days prior to receiving 10 mg/day.
 - The target dose is 10 mg/day, however, the investigator has the possibility to increase the dose to a maximum of 20 mg/day in case of unsatisfactory response or decrease the dose to 5 mg/day in case of dose-limiting AEs. The dose can be up- or down-titrated with 5 mg/day. The patient should receive the same dose for 2 days before being up- or down-titrated to a new dose. Changes in dosing may occur at any visit during the first 8 weeks at the investigator's discretion. In addition, between Week 2 and Week 8, the patient and/or parent(s)/legal representative(s) can request an unscheduled visit to discuss their current dose. The minimum dose is 5 mg/day.
- From Week 8 and onwards the dose has to remain fixed.
- Patients in remission (CDRS-R total score ≤ 28) at both Weeks 10 and 12 or with an adequate clinical response (defined as $\geq 50\%$ reduction in the CDRS-R total score compared to the baseline score in this study [subtracted 17 as 17 is the minimum CDRS-R Total Score] and a CDRS-R total score ≤ 35) at both Weeks 10 and 12 will be randomized in the Double Blind, placebo-controlled, fixed-dose period.

- Patients who do not fulfil randomization criteria for remission or adequate response at Week 10 and/or Week 12 will be withdrawn from the study and will complete an early Withdrawal Visit. Non-remitters/non-responders who leave the study will be treated at the investigator's discretion.

A Safety Follow-up Visit will be performed approximately 4 weeks after withdrawal from the Open Label Period.

[figure not shown]

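### SAP 11.1 measures the open-label CDRS-R change from randomization (Week 12), so the change column runs backward and has no defined reference for children never randomized

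*SAP*

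**What the plan says.** SAP 11.1, below Panel 3, adds a CDRS-R summary for the open-label phase to the efficacy analyses on the FAS. It promises descriptive statistics, and also that "the change from randomization in the CDRS-R total score, per inclusion source, will be presented for the Open Label Period". The sentence names no analysis set.

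SAP 4.1 defines two reference points:

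- **Randomization (Visit):** "baseline for the primary analysis will be defined as the randomization visit, i.e. the start of the Double-Blind treatment period".
- **Baseline (Visit):** "For the analysis of safety, baseline is defined as the start of the Open Label Period", for *de novo* and 12709A rollover patients.

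SAP 4.2 puts the randomization visit at Visit 8, after the 12-week open-label period. SAP 3.1 measures the response criterion for randomization as a "reduction in the CDRS-R total score compared to the baseline score in this study". It also says: "Patients who do not fulfil randomization criteria for remission or adequate response at Week 10 and/or Week 12 will be withdrawn from the study".

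**The concern.** Randomization and Baseline are separately defined terms in the SAP, and SAP 11.1 uses the one that falls at the end of the period it is meant to describe. A programmer who follows the text would subtract the Week 12 score from the scores that precede it. There would be no defined value to subtract for a child who was withdrawn before randomization.

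What is at stake is the readability of one descriptive column. It belongs to the only open-label efficacy summary in SAP section 11, and it describes the phase that selects the randomized population. A programmer who corrected the phrase without comment would depart from the SAP, and SAP section 1 requires deviations to be described and justified in an amendment or the study report.

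**Working it through.** **1. The plan's own figures.** Protocol 16.10 says: "To achieve 80 randomized patients, 150 patients are estimated to be enrolled into the study". That is 80/150 = 53.3% overall. The same section expects about 60% of *de novo* patients to qualify.

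The power statement can be reproduced:

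- Hazard ratio = ln(1 − 0.69) / ln(1 − 0.42) = 2.150.
- Expected events = 40 × (0.42 + 0.69) = 44.4.
- Schoenfeld power at one-sided 5% = 81.7%, in line with the stated figure of at least 80%. Freedman's approximation gives 78.5%.

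These inputs concern randomized patients only, and nothing in the open-label table enters them.

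**2. Direction of the change score.** In the open-label schedule (Protocol Panel 2; SAP Appendix II), Visits 2 to 7 precede Visit 8. The scores below are assumed, for illustration only.

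| Week | Score | Change from randomization (score − 26) | Change from Baseline (score − 60) |
|---|---|---|---|
| 0 | 60 | +34 | 0 |
| 4 | 45 | +19 | −15 |
| 8 | 35 | +9 | −25 |
| 10 | 28 | +2 | −32 |
| 12 | 26 | 0 | −34 |

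A 34-point improvement appears as positive values falling to zero. On the CDRS-R higher is worse, so a reader would normally take a positive change as deterioration.

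**3. Children without a defined reference.** The 80 to be randomized include direct rollovers from 12712A (Protocol synopsis, number of patients planned). Their number is not stated; call it k.

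- **Protocol reading.** The 150 are *de novo* and 12709A patients only, so all are open-label entrants. Never randomized = 150 − (80 − k) = 70 + k. This is 70 at k = 0, 80 at k = 10 and 90 at k = 20.
- **SAP section 3 reading.** The 150 also include 12712A patients. Open-label entrants = 150 − k, and never randomized = (150 − k) − (80 − k) = 70 for any k.
- **60% qualification rate applied to all 150.** This is an assumption, because the rate is stated for *de novo* patients. Not qualifying = 0.40 × 150 = 60.

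The supportable range is therefore roughly 60 to 70 or more. The middle figure of 70 is 70/150 = 46.7% of those enrolled.

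**4. Whether another section repairs it.**

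- SAP 4.1 gives the open-label Baseline for safety only.
- SAP section 5 and 11.2 tie efficacy analyses to the FAS, which holds only randomized patients.
- Other open-label outputs use the APES: baseline characteristics (section 8), concomitant medication (section 9), exposure (section 10) and safety (section 12).
- No section gives another reference point for the open-label CDRS-R change.

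**The case against.** The strongest reply is that this is a wording slip with little consequence. In its efficacy text the SAP replaces the protocol's term baseline with randomization (compare Protocol 16.8.4 with SAP 11.4.1), and the word was probably carried into this sentence. Open-label CDRS-R change is not a listed endpoint in either document. The table templates are in a separate document that is not available here, so what will actually be programmed is unknown. All of this stands and limits the weight of the point. It does not make the sentence correct.

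Three stronger readings are tempting, and the documents do not support them:

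- **That the summary cannot show open-label improvement, or covers only selected responders.** The sentence promises descriptive statistics as well as the change. Footnote a to Panel 3 treats absolute values and changes as separate items. Absolute scores by visit need no reference visit, can include children never randomized, and would show a fall. Even the change column holds the right size of change, with the sign reversed, for children who have both values.
- **That no value exists for anyone not randomized.** CDRS-R is scheduled at Visit 8, where the randomization criteria are checked, and also at the Withdrawal Visit. SAP 16.1.1 maps Withdrawal Visit scores to nominal visits, and Panel 6 labels Visit 8 the end of the open-label period. A child who fails at Week 12 may therefore have a Visit 8 score. Under SAP 4.1 that score is not a randomization value, because the child never enters the double-blind period.
- **That 70 is a firm minimum.** Applying the 60% rate to all 150 gives 60. Direct 12712A rollovers raise the count above 70 only on the protocol's reading of the 150.

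**Conclusion.** The point holds for the change score. As written, it uses a reference that comes after the data it describes, so its sign is reversed. It also has no defined reference for roughly 60 to 70 or more of about 150 enrolled children. That range rests on approximate planning counts, an unstated number of direct 12712A rollovers and, at the lower end, a qualification rate stated only for *de novo* patients.

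A reader might infer that the trial's efficacy conclusions are touched; they are not. The table is descriptive. The primary Cox analysis, its power, and the double-blind change scores, for which randomization is the right reference, all stay as they are. This is a low-priority correction, worth making because the rule as stated gives a wrong output.

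**What to change.** Two edits are needed:

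1. In SAP 11.1, replace the phrase with: *change from Baseline (Visit 2) in CDRS-R total score by visit, per inclusion source and overall, on the APES*.
2. In SAP 4.1, extend the open-label Baseline definition to cover open-label efficacy summaries. Without this, the first edit would rely on a baseline that the SAP defines only for safety.

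The CDRS-R is already scheduled at Visit 2 for *de novo* patients, and the 12709A completion value serves for those rollovers. Every open-label patient with a Visit 2 score then has a reference. The cost is a phrase in each of two SAP sections and a matching check of the table template. No data collection, sample size or confirmatory analysis changes.

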11.2 General Efficacy Analysis Methodology

All the statistical tests of the efficacy endpoints will be one-sided tests performed at the 5% significance level and all confidence intervals (CIs) will be 95% CIs, unless otherwise specified.

For all proposed analyses the applicable assumptions will be checked before the respective analysis is carried out.

The efficacy analyses will be based on the FAS for the Double-Blind Treatment Period. The SAS code for the statistical analyses is provided in [Appendix III](#).

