16.8 Efficacy Analyses

16.8.1 General Efficacy Analysis Methodology

All the statistical tests of the efficacy endpoints will be two-sided tests performed at the 5% significance level and all confidence intervals (CIs) will be 95% CIs, unless otherwise specified.

The efficacy analyses will be based on the FAS.

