16.8.2 Primary Analysis of the Primary Endpoint

The primary efficacy analysis will compare the time to relapse in the double-blind period between vortioxetine and placebo treated patients. Relapse will be defined as either a total score ≥ 40 on the CDRS-R with a history of 2 weeks of clinical deterioration, or clinical deterioration as judged by the clinician and documented in the eCRF.

The two treatment groups will be compared using a Cox regression model with exact adjustment for ties.

The regression model will have treatment as fixed factor, CDRS-R Total Score at randomization as covariate, and separate baseline hazards for the stratification factor, i.e. the patient inclusion source (*de novo* patients, rollover patients from 12709A, or from 12712A). Further details will be given in the SAP.

A one-sided 5% level of significance will be used. Patients not relapsing before Week 26 will be censored at Week 26 and patients withdrawing due to other reasons than relapse will be censored at time of withdrawal.

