16.8.3 Sensitivity Analyses of the Primary Endpoint

The following sensitivity analyses will be performed:

1. The primary analysis will be repeated ignoring relapses occurring during the first week, two weeks and four weeks of the double-blind period, respectively.
2. The number of relapses will be summarized according to relapse criteria: CDRS-R total score ≥ 40 with 2 weeks of clinical deterioration, investigator's judgement, or both.
3. Primary analysis will be repeated for the *de novo* patients and for the (pooled) 12709A patients and 12712A patients.

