16.8.5 Testing Strategy

This section is not applicable.

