16.8.6 Analysis of the Exploratory Endpoint(s)

No formal exploratory endpoints have been defined.

On an exploratory basis, severity of illness, gender and age will be assessed as covariates or to generate subgroups for the Cox regression model as described in section [16.8.2](#).

In addition, descriptive statistics will be used to compare patient populations and treatment outcome between the geographical regions.

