11.3.2 Sensitivity Analyses of the Primary Endpoint

The following sensitivity analyses will be performed:

1. The primary analysis will be repeated ignoring relapses occurring during the first week, two weeks and four weeks of the Double-Blind Treatment Period, respectively.

For the purpose of this sensitivity analysis 3 subsets of data will be defined:

- i) A subset excluding all patients with a relapse within the first 7 days after the start of the Double-Blind Treatment Period.
- ii) A subset excluding all patients with a relapse within the first 14 days after the start of the Double-Blind Treatment Period.
- iii) A subset excluding all patients with a relapse within the first 28 days after the start of the Double-Blind Treatment Period.

The primary analysis of the study, as described, will be repeated in each of the 3 subsets above and for each subset the hazard ratio for vortioxetine compared to placebo will be estimated from the model and presented with p-values and 95% CIs.

2. The primary analysis will be repeated for the *de novo* patients and for the (pooled) 12709A patients and 12712A patients additionally.

The hazard ratio's for vortioxetine compared to placebo will be estimated from the model and presented with p-values and 95% CIs for *de novo* and rollover patients (pooled 12709A and 12712A) separately.

On an exploratory basis, if feasible, the impact of the use of psychotherapy, severity of illness, gender and age may be investigated. Therefore, these may be added as fixed factors or covariates to the Cox regression model, or subgroups may be created.

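### SAP 11.2 makes one-sided 5% the default for all efficacy tests, where protocol 16.8.1 makes it two-sided 5% and excepts only the primary Cox analysis

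*SAP*

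**What the plan says.** Protocol 16.8.1 gives the general rule: "All the statistical tests of the efficacy endpoints will be two-sided tests performed at the 5% significance level". It adds 95% confidence intervals and allows for exceptions where specified. Protocol 16.8.2 specifies one for the primary Cox analysis: "A one-sided 5% level of significance will be used". The synopsis says the same. Protocol 16.8.4 gives no sidedness for the relapse logistic regression, the MMRM or the ANCOVA, so the two-sided default governs them. On a testing strategy, protocol 16.8.5 says only: "This section is not applicable".

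SAP 11.2 gives the general rule as "All the statistical tests of the efficacy endpoints will be one-sided tests performed at the 5% significance level", again with 95% intervals and the same allowance for exceptions. SAP 11.3.1 repeats one-sided 5% for the primary analysis. SAP 11.4.1, 11.5 and Appendix III do not mention two-sided testing, so under the SAP the secondary tests are one-sided.

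**The concern.** The two general rules contradict each other, and the SAP is the document from which the analysis is run. SAP 11.3.1 already sets one-sided 5% for the primary analysis, so the changed default in 11.2 is not needed to protect it. Its effect falls on the other efficacy tests.

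At stake is which secondary results may be called significant. A favourable result with a two-sided p-value between 0.05 and 0.10 passes under the SAP and fails under the protocol, and the looser rule favours vortioxetine. The analysis that matters most is the relapse logistic regression. Relapse is the named secondary endpoint under the primary objective, and its analysis is not labelled exploratory.

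**Working it through.** **1. The primary design, to see whether it is part of the conflict.** Inputs from protocol 16.10 and SAP 14: relapse rates 0.42 and 0.69 over 26 weeks, 40 per group, one-sided 5%, at least 80% power, hazard ratio 2.15.

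- Hazard ratio: ln(1 − 0.69) / ln(1 − 0.42) = 2.150, as stated.
- Expected events without dropout: 40 × 0.42 + 40 × 0.69 = 44.4.
- Schoenfeld power: Φ(√44.4 / 2 × ln 2.15 − z) = Φ(2.550 − z).
  - One-sided 5%, z = 1.645: 81.7%.
  - Two-sided 5%, z = 1.960: 72.3%.
- A Lakatos-type log-rank calculation (exponential hazards, 26 weeks, no dropout) gives 81.0% and 71.4%.

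The stated power reproduces at one-sided 5% and not at two-sided 5%. The primary test is one-sided by design in both documents, so the conflict lies elsewhere.

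**2. Analyses affected.** From SAP Panel 3:

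- relapse logistic regression, observed cases and LOCF: 2;
- five scores (CDRS-R total, PQ-LES-Q total, PQ-LES-Q item 15, CGI-S, CGI-I), each by ANCOVA and MMRM: 5 × 2 = 10, all labelled exploratory.

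The critical value for each is 1.645 under the SAP and 1.960 under the protocol. The nominal error in favour of vortioxetine is 5% against 2.5%.

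**3. Size for the relapse comparison.** Let x and y be the relapses on vortioxetine and placebo, 40 per arm. The statistic is the signed root of the likelihood-ratio statistic, z(x, y) = sign(y − x) × √(2 Σ O ln(O/E)), which matches the profile-likelihood interval in SAP 11.4.1. The binomial probabilities are summed over all (x, y) with z > 1.645 (SAP) or z > 1.960 (protocol, in favour of vortioxetine). There is no adjustment for inclusion source or CDRS-R.

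| True relapse rates (vortioxetine, placebo) | SAP rule | Protocol rule | SAP only |
|---|---|---|---|
| 0.42, 0.69 | 78.4% | 70.8% | 7.6% |
| 0.42, 0.42 | 4.67% | 2.71% | 1.97% |
| 0.555, 0.555 | 4.65% | 2.77% | 1.88% |
| 0.69, 0.69 | 5.29% | 2.69% | 2.60% |

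The counts are discrete, so a smooth check is useful. With the pooled rate 0.555:

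- SE under no effect: √(0.555 × 0.445 × 2/40) = 0.1111.
- SE at the design rates: √((0.42 × 0.58 + 0.69 × 0.31)/40) = 0.1069.
- Power: Φ((0.27 − z × 0.1111) / 0.1069) = 79.3% at z = 1.645 and 68.7% at z = 1.960, a gap of about 10.5 percentage points.

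**4. An example.** Suppose 28/40 relapse on placebo, close to the design rate. With 20/40 on vortioxetine, the odds ratio is (20/20)/(28/12) = 0.43, z = 1.833, one-sided p = 0.033 and two-sided p = 0.067. This is significant under the SAP and not under the protocol. With 19/40, z = 2.054 and two-sided p = 0.040, so both rules are met.

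**The case against.** The strongest reply is that little in the plan depends on this rule. SAP 11.4.1 asks for odds ratios with 95% intervals and requests no p-values for the secondary analyses, whereas the Cox sections (11.3.1, 11.3.2, 11.5) do request them. The score endpoints are exploratory, no testing strategy applies, and the primary test is the same in both documents. All of this stands and keeps the point minor. It does not remove the conflict: 11.2 still governs every efficacy test, and the relapse logistic regression is not exploratory.

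Three stronger readings are tempting, and the documents do not support them.

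- *The 95% intervals reported beside one-sided tests are a further harm.* A one-sided 5% result can indeed have a 95% interval that includes no effect. But the primary Cox analysis has the same pairing by design (SAP 11.3.1), so this is not a separate consequence of 11.2.
- *The documents settle which repeats of the primary analysis are one-sided.* They do not. Protocol 16.8.3 says "The primary analysis will be repeated ignoring relapses occurring during the first week" and gives no sidedness. SAP 11.5 uses similar repeat language for the two separate relapse definitions. For those definitions the protocol plans only a count: "The number of relapses will be summarized according to relapse criteria". Inheriting the primary rule and taking the default are both arguable.
- *The gap is much larger if some outcomes are missing.* Enumeration at smaller evaluable numbers moves up and down with the coarseness of a 2×2 table, and the documents give no evaluable number. Only the 40-per-arm figures are used here.

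**Conclusion.** Wrong as written, minor. The contradiction between SAP 11.2 and protocol 16.8.1 is literal, and it is clear for the relapse logistic regression and the exploratory MMRM and ANCOVA analyses. For the relapse comparison, the two rules disagree in favour of vortioxetine in about 8% of trials (exact) or 10% (normal approximation) at the design rates, and in about 2 to 2.6% with no effect. These figures assume 40 evaluable patients per arm and an unadjusted comparison. The planned model adjusts for inclusion source and CDRS-R at randomization, so they indicate the order of size only.

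A reader might infer that the one-sided primary test is itself a mistake, or that the trial's main conclusion is at risk. Neither follows: one-sided 5% for the primary analysis, 80 patients and the stated power agree across protocol and SAP. The consequence is limited to which secondary results may be called significant.

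**What to change.** In SAP 11.2, restore the protocol's default, "All the statistical tests of the efficacy endpoints will be two-sided tests performed at the 5% significance level", and name the primary analysis of time to relapse (11.3.1, one-sided 5%) as the exception. Leave the 95% intervals as they are.

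The sponsor should also state one consistent rule for the analyses described as repeats of the primary analysis, in both 11.3.2 and 11.5. The exploratory covariate and subgroup Cox models ("On an exploratory basis, if feasible, the impact of the use of psychotherapy, severity of illness, gender and age may be investigated") state no sidedness of their own in either document and would take the restored default unless the sponsor says otherwise.

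The cost is a short text change in the SAP before unblinding, with no protocol amendment, no extra patients and no change to the primary test. The downside is that secondary tests are somewhat less likely to reach significance: for the relapse comparison at the design rates, 70.8% instead of 78.4%.
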